6.1.3 PRIMARY AND SECONDARY STUDY ENDPOINTS

PRIMARY STUDY ENDPOINT

The capability of PulmoVista 500 for continuous monitoring of ventilation and its changes at different points in time during varying states of regional ventilation, the cross-correlation function (CCF) between global tidal impedance (EIT) waveforms and global tidal volume (ventilator) curves will be evaluated.

SECONDARY STUDY ENDPOINTS

- First secondary endpoint: To assess the capability of PulmoVista 500 to detect changes in regional ventilation by evaluating the cross correlation between impedance waveforms derived from PulmoVista 500 and volume curves derived from ventilator during one-lung-ventilation.
- Assess that changes of tidal volumes induced by ventilator settings can be monitored by the "Trends view"
- Assess that changes of the end-expiratory lung volumes (induced by e.g. PEEP changes, recruitment and suctioning maneuvers) can be monitored by "dELLI trend view"

- Documentation of any safety events related to the use of PulmoVista 500
- Assessing the use specific clinical helpfulness of PulmoVista 500 - clinical helpfulness of PulmoVista 500 is proven if
 - see attachments (chapter 23.1) clinical usability

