7 STATISTICAL CONSIDERATIONS

7.1 SAMPLE SIZE, DROP-OUT-RATES, LEVEL OF SIGNIFICANCE AND POWER OF THE CLINICAL INVESTIGATION

Primary Endpoint (Efficacy)

Based on former porcine trials⁷ with PulmoVista 500 and data from clinical studies with other EIT devices the sample size was calculated using the program G*Power 3.1.9.2.

An α -error of $p = 0.05$ and a power = 0.9 in a two-sided testing resulted in a sample size of 68 patients. With this sample size a difference of 0.1 of the mean cross-correlation coefficient shall be detected, i.e. the true value of a calculated mean of 0.8 will not be smaller than 0.7 and not be larger than 0.9 with the given p-value and power under the assumption of a standard deviation of less than .25.

Accounting for 15 % potential drop-outs 80 patients shall be enrolled in the study.

Secondary Endpoint (Efficacy)

Based on former porcine trials with PulmoVista 500 and data from clinical studies with other EIT devices the sample size was calculated using the program G*Power 3.1.9.2. An α -error of $p = 0.05$ and a power = 0.9 in a two-sided testing resulted in a sample size of 22 patients. With this sample size a difference of 0.1 of the proportion between reference and investigated variable shall be detected.

Accounting for 15 % potential drop-outs 25 patients shall be enrolled in this subgroup of the study.

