23.2 Clinical Plausibility Questionnaire

Questions addressing the regional aspects of the secondary endpoints

One of the major purposes of the pivotal clinical study

Assessment of the capability of PulmoVista 500 to continuously monitor changes of ventilation over time is to assess the plausibility of the regional information, which cannot be validated by CT scans.

The following questions are intended to validate, whether

- the regional information provided by PulmoVista 500 is plausible in the presence of certain lung conditions, which are visible in CXR or lung CT and known to cause poor ventilation
- PulmoVista 500 is capable of displaying changes of lung conditions induced by therapeutic interventions
- those changes are plausible and correspond to the information that an experienced user would expect based on his knowledge about lung physiology

Please respond the following questions in eCRF if this does not interfere with your clinical routine.

1. Select the view „**Main**“.
Does the **Tidal Image** indicate poorly or non-ventilated lung regions and does this location approximately match with those regions, where CXR or lung CT shows either lung collapse, atelectasis or pleura effusion?

2. Select the view "**Main**" and observe the Tidal Image, while one of the lungs is blocked.
Does the **Tidal Image correctly** indicate which side of the lung is not being ventilated?
3. Open the view "**dELLI trend**" after the PEEP setting has been changed. Set C1 at the lower and C2 at the higher PEEP level.
Does the image dELLI: C2 minus C1 show the expected increase of endexp.lung volume in turquoise (light blue) color?
4. Open the view "**End-insp. trend**" after the PEEP setting has been changed significantly (2 mbar or more). Set C1 at the lower and C2 at the higher PEEP level.
Does the image Change: C2 minus C1 and/or the corresponding regional Tidal Variations show the expected redistribution of ventilation from ventral to dorsal?
5. Open the view "**dELLI trend**" after lung suction has been conducted. Set C1 at a phase before and C2 during or immediately after the lung suction.
Does the image dELLI: C2 minus C1 show the expected decrease of lung volume in orange color?
6. Select the view "**Main**" and observe the Tidal Image from a patient with pneumonectomy.
Does the Tidal Image properly indicate the non-ventilated lung regions and does the location approximately match with those region, where the lung has been removed?

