5 STATISTICAL ANALYSIS

5.1 PARTICIPANTS

A sample size of n=80 patients (including at least 25 patients for the OLV subgroup) has been calculated with an assumed drop-out rate of 15%.

OLV subgroup consists of patients who have been scheduled for surgical procedures that require the ventilation of only one lung (e.g., intubation using a double-lumen tube or placement of a bronchus blocker).

The remaining 55 patients are patients mechanically ventilated in an intensive care unit (ICU) via an artificial airway access (endotracheal tube or tracheostomy tube). For those, it can be assumed that significant changes to the ventilation settings will have to be made, which are continuously recorded with the PulmoVista 500 during the study.

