From this table, the success rate $(a + d) / (a + b + c + d)$, the sensitivity $a / (a + b)$, the specificity $d / (c + d)$ and the corresponding confidence intervals are calculated. The reverence (real side of the ventilation) is taken in the study documentation (e.g. Name of corresponding Marker and/or MACRO Database) of the individual patients.

- To assess the ability of PulmoVista 500 to display changes in ventilation-induced tidal volumes through the "Trend View", the plausibility questionnaire across all patients is evaluated. The questions of the plausibility questionnaire in relation to the "main view" are individually counted according to their categories (yes / no / n.a.) and listed as a percentage.
- To assess the ability of PulmoVista 500 to display changes in end-expiratory lung volumes (induced by e.g. PEEP changes, recruitment and suction maneuvers) using the "dELLI Trend View", the plausibility questionnaire is evaluated across all patients. The questions of the plausibility questionnaire in relation to the "dELLI trend view" are individually counted according to their categories (yes / no / n.a.) and listed as a percentage.
- The evaluation of clinical usefulness, the nine questions of the questionnaire on clinical usefulness, are individually counted according to their category level (1 very difficult ... to ... 5 very useful) and listed on a percentage basis. Furthermore, the mean and standard deviation are calculated for each of these nine questions.

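### The tidal-volume/Trends-view endpoint is answered from main-view questions that do not address it, question 4 is left unanalysed, and the plausibility percentages have no stated denominator

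*SAP*

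**What the plan says.** Protocol 6.1.3 sets a secondary endpoint: "Assess that changes of tidal volumes induced by ventilator settings can be monitored by the" Trends view. The same endpoint in the Protocol synopsis points to the questionnaire in chapter 23.2. A separate endpoint concerns end-expiratory lung volume in the dEELI trend view.

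SAP 3.3.1 restates the tidal-volume endpoint with the main view in place of the Trends view. SAP 5.6.1 returns to the Trend View when stating the aim, but counts the main-view questions. For the dEELI endpoint it counts the dEELI questions. In both cases all patients are the stated population (for dEELI: "the plausibility questionnaire is evaluated across all patients"), and the answers are "individually counted according to their categories (yes / no / n.a.) and listed as a percentage". No denominator, interval or rule for blank answers is given, and the table shells in SAP 7.4 are empty.

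The questions in Protocol 23.2 are conditional. Question 2 asks the user to "observe the Tidal Image, while one of the lungs is blocked". Question 6 asks the user to "observe the Tidal Image from a patient with pneumonectomy". The others need an imaging finding, a PEEP change or suctioning. Users are asked to answer only if their clinical routine allows it.

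On numbers, SAP 5.1 says: "A sample size of n=80 patients (including at least 25 patients for the OLV subgroup) has been calculated with an assumed drop-out rate of 15" per cent. It places the other 55 patients in intensive care.

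**The concern.** There are two separate problems.

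The first is that the endpoint and the data counted for it do not match. The questionnaire is the only analysis planned for the tidal-volume/Trends-view endpoint. If the plan is followed exactly, that endpoint is reported from items about where poorly ventilated regions lie, which lung is blocked and where a lung has been removed. The one item that compares ventilation before and after a setting change in a non-dEELI trend view is collected and then not used.

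The second is the denominator. A percentage over all patients with n.a. as a category does not estimate how often the display was plausible where the question could be asked. A reader who sees a low yes percentage cannot tell without further arithmetic whether the display failed or the question seldom applied. Because answering is optional, blanks may also be mixed with n.a.

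These percentages are the only results for two secondary endpoints. Protocol 23.2 describes plausibility of the regional information as a major purpose of the study, and Protocol 3.2 expects the data to support authorisation in other countries.

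**Working it through.** **Planned numbers.** Protocol 7.1 gives two-sided alpha 0.05, power 0.90, a difference of 0.1 and an SD of 0.25, so d = 0.1/0.25 = 0.4. A one-sample t-test with the noncentral t distribution needs n = 68 (power 0.902); the normal approximation gives 66. This reproduces "power = 0.9 in a two-sided testing resulted in a sample size of 68 patients". Inflating for drop-out, 68/(1 − 0.15) = 80. The documents contain no plausibility percentage to reproduce.

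**Questions against endpoints** (Protocol 23.2 and SAP 5.6.1):

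| Question | View | Condition | What is asked | Counted in SAP 5.6.1 for |
|---|---|---|---|---|
| 1 | Main | Finding on chest X-ray or CT | Location of poor ventilation | Tidal-volume endpoint |
| 2 | Main | One lung blocked | Which side is unventilated | Tidal-volume endpoint |
| 3 | dEELI trend | PEEP change | Rise in end-expiratory volume | dEELI endpoint |
| 4 | End-insp. trend | PEEP change of 2 mbar or more | Ventral-to-dorsal redistribution | Nothing |
| 5 | dEELI trend | Suctioning | Fall in lung volume | dEELI endpoint |
| 6 | Main | Pneumonectomy | Location of the missing lung | Tidal-volume endpoint |

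Questions 1, 2 and 6 do not compare two ventilator settings. Question 4 does, but it asks about regional redistribution after a PEEP change, so it covers only part of the endpoint. The usability questionnaire in Protocol 23.1 also uses the End-insp. trend view, but it asks about ease and usefulness, and the SAP assigns it to a different endpoint.

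**Denominator.** Let N be all patients, m those to whom a question applies (all answering yes or no), and y the number of yes answers. Then

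all-patient percentage = y/N = (m/N) × (y/m); rate where applicable = y/(yes + no) = y/m.

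Intervals are exact (Clopper–Pearson). When y = m, the lower 95% limit is 0.025^(1/m); for m = 25 this is 0.863.

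| Case | m | y | N | y/N | y/m (95% CI) |
|---|---|---|---|---|---|
| Question 2, planned OLV number | 25 | 25 | 80 | 31.3% | 100% (86.3 to 100) |
| Question 2, 20 correct | 25 | 20 | 80 | 25.0% | 80.0% (59.3 to 93.2) |
| Question 2, 22 evaluable (Protocol 7.1) | 22 | 22 | 80 | 27.5% | 100% (84.6 to 100) |
| Same, 68 evaluable in total | 22 | 22 | 68 | 32.4% | 100% (84.6 to 100) |
| Assumed subset | 10 | 10 | 80 | 12.5% | 100% (69.2 to 100) |
| Assumed subset | 5 | 5 | 80 | 6.3% | 100% (47.8 to 100) |
| Assumed subset | 2 | 2 | 80 | 2.5% | 100% (15.8 to 100) |

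Only question 2 has a subset size in the documents; the last three rows are assumptions. A subset could also be large. If every planned ICU patient and no OLV patient had a PEEP change, the all-patient ceiling would be 55/80 = 68.8%.

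**Recoverability.** With 20 yes, 5 no and 55 n.a., the listed percentages are 25.0, 6.25 and 68.75, and 25.0/(25.0 + 6.25) = 80.0%. The applicable rate can therefore be recovered. A response rate cannot, because blanks are not shown apart from n.a.

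**The case against.** The strongest reply concerns the denominator. The SAP never says that yes is divided by all patients including n.a.; that is the natural reading, not the text. A yes/no/n.a. distribution is arithmetically sound, shows inapplicability openly and lets a reader recover yes/(yes+no). The summaries carry no test, and Protocol 7.3 defines no pass/fail criterion. Left/right discrimination, which question 2 addresses, has its own analysis by blinded raters with confidence intervals, so a misread question 2 percentage would not leave that capability unassessed. The OLV number is a minimum, so 31% is not a strict ceiling. All of this stands. The percentages cannot be called wrong; they are under-specified.

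A reader might also infer that the applicable subsets are small. The documents do not show this: PEEP trials, recruitment and suctioning are among the listed ICU interventions, and no counts are given. Nor do the figures depend on case mix rather than on the device. In y/N = (m/N) × (y/m) both parts count, and 25 against 20 correct answers moves the all-patient figure from 31.3% to 25.0%.

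Finally, it is fair to object that question 4 is no full substitute, since it concerns redistribution after PEEP changes. That limits the remedy, but it does not make the main-view questions relevant to the endpoint. None of these replies repairs the mismatch between endpoint and questions.

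**Conclusion.** The concern holds in two parts of different weight.

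The mismatch is the firmer part. SAP 3.3.1 and 5.6.1 disagree with each other and with Protocol 6.1.3 on the view. The questions counted do not address a change after a ventilator setting, and question 4 is in no analysis. Recomputing the percentages cannot cure this. Linking question 4 to the endpoint assumes that the Trends view means the End-insp. trend view, the only non-dEELI trend view in the Protocol 23.2 questionnaire; the sponsor should confirm this.

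The denominator part is a gap in specification. On the all-patient reading, with 25 applicable patients out of 80, perfect performance on question 2 shows as about 31% yes instead of 100% (exact 95% CI 86.3 to 100). For the other questions the size cannot be stated. The stronger claim, that the planned percentages are wrong, is not supported, because the SAP fixes no denominator and the counts permit the right calculation.

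The results are descriptive and no formal decision depends on them. This is a correction worth making before analysis; it does not threaten the primary result.

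**What to change.** In SAP 3.3.1 and 5.6.1:

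- Name one view for the tidal-volume endpoint and make it agree with Protocol 6.1.3.
- Analyse question 4 under that endpoint, stating that it covers only regional redistribution of tidal variation after a PEEP change and is therefore a partial measure.
- Report questions 1, 2 and 6 separately, as plausibility of regional information.
- For every question, give yes/(yes+no) with n and an exact 95% confidence interval. Show n.a. and unanswered as separate counts, because completion is optional. This brings the questionnaire closer to the OLV rater analysis, where unresolved not-assessable cases leave the 2x2 table and rates carry intervals.

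The cost is SAP wording and a table shell; no new data are needed. Intervals will be wide where few patients qualify: with five applicable patients, all yes, the lower limit is 47.8%. The sponsor may also have to report the tidal-volume endpoint as only partly addressed, since no question measures it fully.

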5.6.2 Safety / Compatibility

5.6.2.1 Adverse events

Information on AEs will be collected from the time of enrollment until regular completion of study, death or withdrawal (whichever comes first).

The investigator will report all AEs as soon as possible (preferably within 7 days) to their knowledge by entering them in the eCRF.

AEs are documented on an AE form (eCRF). Diagnosis, onset, and end of the AE, seriousness, severity, causal relationship with the investigational medical device, with the study procedures, treatment of the AE, and the outcome of the event will be documented. The Investigator will follow-up the event until the AE has been resolved, resolved with sequelae or was fatal.

All AEs will be listed in the final report with the above criteria.

5.6.2.2 Laboratory parameters

If measured, the saturation of s_aO_2 , s_pO_2 , p_aO_2 , p_aCO_2 , FiO_2 before and after the intervention are documented and displayed with their distribution.

5.6.2.3 Vital signs

Height, weight, BMI, systolic and diastolic blood pressure, heart rate and chest circumference are recorded and displayed with their distribution parameters.

5.7 SUBGROUP ANALYSIS

Depending on the type of ventilation there are 2 subgroups:

- ICU patients (planned number 55) mechanically ventilated in an intensive care unit via an artificial airway access (endotracheal tube or tracheostomy tube), which are expected to require significant changes in ventilation settings, occur before, during and after changing the ventilation settings with PulmoVista 500. The changes in ventilation settings should be reflected in noticeable changes in ventilation distribution.
- OLV patients (planned number 25) enrolled for surgical interventions requiring ventilation of only one lung (single-lung ventilation) (e.g., intubation using a double-lumen sub- stance or placement of a bronchus blocker).

For the different questions of the study, either the entire collective or the separate subgroups are analyzed.

5.8 INTERIM REPORTS

Interim reports are not planned.

6 SOFTWARE

Programm Dräger EIT Data Analysis Tool 6.1

SAS

SPSS

EDITOR for Windows

EXCEL

7 APPENDIX

7.1 REFERENCE VALUES OF LABORATORY PARAMETERS

[figure not shown]
Omitted

7.2 WORKFLOW FOR DETERMINING THE TIME RANGES USED TO CALCULATE THE CROSS CORRELATION BETWEEN THE GLOBAL IMPEDANCE WAVEFORM (PULMOVISTA 500) AND THE VOLUMETRIC WAVEFORM (EVITA V500).

Workflow for determining the time ranges used to calculate the cross correlation between the global impedance waveform (PULMO VISTA 500) and the volume waveform (EVITA V500)

[figure not shown]
Step Description

- 1 Open EIT Data Analysis Tool SW 6.1
- 2 Use the **Load** button to load the first file in the series containing the intervention to be evaluated; the beginning and the type of intervention are marked by an event marker (see example below)
- 3 Use the button **Sequence to ...** to load the last file of the series containing the intervention to be evaluated
- 4 Record the total length of the loaded files (time scale below ROI 4)

[figure not shown]
5 Select the files (1 min each) that lie directly before (1) or after (2) the intervention, in which a uniform impedance waveform, and in particular no artifacts, can be seen and in which no parts of the intervention itself are contained.

Example: series of 10 files per 1 min, in which the interventions took place between min 3 and 4.

[figure not shown]

6 Place cursor in the area of file 1 (exact position does not matter, in this example within the third minute)

- 7 Use the buttons **Display ...**, **Time scale** to set the time scale to 60 sec

- 8 Use the button **File ..., save as ASC** to convert the selected file 1 as ASCII file
(the created ASC file is saved in the same directory with the same file name as the selected EIT file, and a two-digit, incremental counter is added to the file name)
- 9 Use the Buttons **Display ...**, **Time scale** to increase the time scale so that the recorded total length is displayed again.
- 10 Place cursor in the area of file 2 (exact position does not matter, in this example within the 5th minute)
- 11 Use the buttons **Display ...**, **Time scale** to set the time scale to 60 sec

- 12 Use the button **File ..., Save as ASC** to convert the selected file 2 as ASCII file
- 13 Now open the two generated ASC files with the statistical evaluation software
- 14 In the area below the line (Image; Time; Global;), Determine the cross-correlation between column C (Global) and column N (~ Volume [ml]).

97	A	B	C	D	E	F	G	H	I	J	K	L	M	N
98	Image	Time	Global	Local 1 (X:16	Local 2 (X:16	Local 3 (X:16	Local 4 (X:15	Min/Max	Event	EventText:	Timing	~Paw [mbar]	~Flow [L/min]	~Volume [m
99	7201	0,51702906	3502,14771	285,251526	1413,7627	1647,13147	155,002075		0	6	0	15,2	-9,4	53 -
100	7202	0,51702964	3483,25464	283,758667	1407,53735	1639,75952	157,199203		0	6	0	15,2	-9,1	44 -
101	7203	0,51703022	3479,07935	282,592102	1403,01392	1634,83862	153,634644		0	6	0	15,2	-8,8	38 -
102	7204	0,5170308	3475,05151	281,994568	1401,00293	1632,85327	160,200729		-1	6	0	15,2	-8,5	29 -
103	7205	0,51703138	3480,70776	282,248383	1402,36475	1634,34448	161,750122		0	6	0	15,2	-8	22 -
104	7206	0,51703196	349,09839	283,65271	1407,53933	1639,89844	163,108002		0	6	0	15,2	-7,8	N 14 -
105	7207	0,51703253	3519,15405	286,490509	1418,46863	1650,09717	164,097702		0	6	0	15,2	-7,7	9 -
106	7208	0,51703311	3555,48242	290,984161	1434,5	1665,42517	154,57312		0	6	0	15,2	-8	3 -
107	7209	0,51703369	3604,16602	297,246277	1456,28699	1686,18213	164,450729		0	6	0	15,2	-7,5	0 -
108	7210	0,51703427	3655,1272	305,242462	1483,71704	1712,43787	163,729797		0	6	0	15,2	-6,8	0 -
109	7211	0,51703485	3737,58008	314,782196	1516,28919	1744,01856	162,490189		0	6	0	15,1	-6,3	0 -
110	7212	0,51703543	3820,07129	325,54129	1553,15466	1780,50732	160,858057		0	6	0	16,4	2,9	0 -
111	7213	0,51703601	3910,58862	337,107178	1593,20581	1821,25232	159,023163		0	6	0	18	26,5	13 -
112	7214	0,51703659	4005,71265	349,030304	1635,18018	1865,39075	157,111557		0	6	0	22,8	49,5	52 -

- 15 For each ASCII file, the correlation is first calculated individually. Subsequently, the correlations of the individual files are then averaged.

7.3 WORKFLOW FOR THE CREATION OF OLV VIDEOS

This workflow describes the creation of the video sequences which are used to assess the capability of PULMO VISTA 500 to monitor regional changes during mechanical ventilation within the OLV-subgroup.

Software:

- Dräger EIT Simulation Tool
- Camtasia Recorder 8
- Camtasia Studio 8

Workflow:

1. Identify the acquisition dates and the patient/site IDs of all OLV patients
2. Identify relevant markers which are set prior and post the induction of one lung ventilation
 - a. document time-stamp of each marker
3. Load EIT-data into *Dräger EIT Simulation Tool*
 - a. Select the “Folder” which contains the acquisition date
 - b. Select the “Subfolder” which contains the relevant patient ID (xx_yyy)
 - c. Select the start-“File” which includes the relating “PRE-Marker”
 - d. Select the “Sequence to file” which includes the relating “POST-Marker”
4. Start *Camtasia Recorder 8*
5. Adjust the recording window according to the size of the “Main”-view
6. Start the simulation within *Dräger EIT Simulation Tool*
7. Start the recording
8. After the simulation has completed one entire loop of simulation, stop the recording
9. Save the recorded video file (use site and patient ID, as well as date of recording) for the definition of the file name
10. Load recorded video file into *Camtasia Studio 8*
11. Crop video sequence according to the previously identified time-stamps of the pre and post markers (the video sequence now contains only the EIT information between the two markers)
12. Process the final video sequence as MP4-file
13. Save the MP4-file containing the respective site and patient ID as well as the date of video processing.

